8.1.2 Primary Analysis Variable for Monotherapy

There is no primary efficacy variable for subjects on monotherapy.

8.1.3 Sensitivity Analyses of the Primary Efficacy Variable

For the subjects who have important protocol deviations who are considered with impact on efficacy, BLOCF (Baseline Observation Carried Forward) will be applied for the post-baseline value.

A summary table based on the FAS_A will be presented:

- Percent Reduction in Partial Seizure Frequency per Week from Baseline to Visit 6 (Analysis Visit 3), by Age Category, Adjunctive Therapy Subjects, (BLOCF)

8.2 Statistical Analysis of the Secondary Efficacy Variables

8.2.1 Secondary Efficacy Variables for Adjunctive Therapy

First Period:

The secondary efficacy variable for subjects on adjunctive therapy for the First Period is the percent reduction in partial seizure frequency per week from Baseline to Study Visit 4 (Analysis Visit 1) and Study Visit 5 (Analysis Visit 2).

Percent reduction in partial seizure frequency per week from Baseline to Study Visit X will be calculated as:

$$\frac{\text{Number of partial seizures per week at Baseline} - \text{Number of seizures per week at Study Visit X}}{\text{Number of partial seizures per week at Baseline}} \times 100$$

If the analysis of the primary efficacy variable, see Section 8.1.1, shows a significant result (lower limit of the 95% confidence interval for the overall group is greater than the predefined threshold of 15.0%), the lower limit of the 95% CI of the median percent reduction in partial seizure frequency at Study Visit 4 (Analysis Visit 1) and Study Visit 5 (Analysis Visit 2) will also be compared with the predefined threshold of 15.0%.

The following summary tables based on the FAS_A will be presented:

- Percent Reduction in Partial Seizure Frequency per Week from Baseline to Visit 4 (Analysis Visit 1), by Age Category, Adjunctive Therapy Subjects
- Percent Reduction in Partial Seizure Frequency per Week from Baseline to Visit 5 (Analysis Visit 2), by Age Category, Adjunctive Therapy Subjects

Combined First and Second Periods:

The secondary efficacy variables for subjects on adjunctive therapy for the combined First and Second Periods are:

- For each analysis visit, percent reduction in partial seizure frequency per week from Baseline.
Note: This is combined over the age categories.
- For each analysis visit, percent reduction in partial seizure frequency per week from Baseline grouped into 6 categories: <0%, 0% to <25%, 25% to <50%, ≥50%, ≥75%, and 100%
Note: This is combined over the age categories.

Percent reduction in partial seizures per week from Baseline at Analysis Visit X will be calculated as:

$$\frac{\text{Number of partial seizures per week at Baseline} - \text{Number of partial seizures per week at Analysis Visit X}}{\text{Number of partial seizures per week at Baseline}} \times 100$$

The calculation of number of partial seizures per week at Baseline is the same as aforementioned (see Section 8.1.1).

Number of partial seizure frequency per week, as collected on the DRC, is calculated at Analysis Visit x, x=1, 2, 3, 4, ..., as:

Number of partial seizures per week at Analysis Visit x = [total number of partial seizures entered on the DRC during the period starting 1 day after Analysis Visit x-1 through Study Day of Analysis Visit x divided by the number of days, within this period, on which data was entered on the DRC] x 7. Those seizure free days (i.e. seizure count is 0 and there is no entry of DRC data) will be included into denominator. Data was NOT entered on DRC only refer to the situation that “Not Done” was ticked on CRF “Seizure Count” page.

The following summary tables based on the FAS_A will be presented:

- Percent Reduction in Seizure Frequency per Week, by Analysis Visit, Adjunctive Therapy Subjects
- Percent Reduction in Seizure Frequency per Week Grouped into 6 Categories by Analysis Visit, Adjunctive Therapy Subjects

8.2.2 Secondary Efficacy Variables for Monotherapy

First Period:

There is no secondary efficacy variable for subjects on monotherapy for the First Period.

Combined First and Second Periods:

The secondary efficacy variables for subjects on monotherapy for the combined First and Second Periods are:

- For each analysis visit, percent reduction in partial seizure frequency per week from Baseline.

Number of partial seizure frequency per week, as collected on the patient dairy form, will be calculated for each Analysis Visit as described in [Section 8.2.1](#) Combined First and Second Periods.

A table [Percent Reduction in Seizure Frequency per Week, by Analysis Visit, Monotherapy Subjects](#) presents summary statistics of subjects for each analysis visit on the FAS_M .
Note: This is combined over the age categories.

- For each analysis visit, percent reduction in partial seizure frequency per week from Baseline grouped into 6 categories: <0%, 0% to <25%, 25% to <50%, ≥50%, ≥75%, and 100% during the combined First and Second Periods.

A table [Percent Reduction in Seizure Frequency per Week, Grouped into 6 Categories, by Analysis Visit, Monotherapy Subjects](#) presents the number and percentage of subjects within each of the above defined six categories for all analysis visits on the FAS_M .
Note: This is combined over the age categories.

8.3 Analysis of Other Efficacy Variables

8.3.1 Derivations of Other Efficacy Variables

The average daily frequency (ADF) of partial seizures as measured by 48h video-EEG will be included as an “other” efficacy variable. Partial seizure count will be based on electrographic seizures with or without clinical correlate depending upon age as specified below. Partial seizures have ILAE seizure code: IA, IB or IC, other seizure codes will not be included in the analysis.

Partial seizure frequency for subjects:

- Aged ≥1 month to ≤6 months will be based on electrographic seizures with an accompanying clinical correlate: item: “Number of electrographic seizures (Partial Onset Seizure only)” and “Number of electro-clinical seizures (Partial Onset Seizure only)” respectively, from Video-EEG CRF. Aged >6 months to <4 years will be based electro-clinical seizures: item “Number of electro-clinical seizures (Partial Onset Seizure only)” from Video-EEG CRF.

The ADF (partial seizures) at Analysis Visit x is defined as:

$$\frac{\# \text{ of partial seizures recorded during the 48 hr video EEG collection period at Analysis Visit } x}{\# \text{ hours of useable video - EEG time at Analysis Visit } x} \times 24,$$

where:

- x = -1 (Baseline), 1, or 3; and
- number of hours of useable video-EEG time = total video-EEG time – disconnection time. Total video-EEG time is defined as the difference between the end and the start of recording date and time. Disconnection time is obtained from the “Video-EEG” CRF (item “Total Disconnect Time”).

Percent reduction in ADF of partial seizure frequency at Analysis Visit 3 (Study Visit 6) compared to Baseline (Study Visit 2) is defined as:

$$\frac{\text{ADF (partial seizures) at Study Visit 2} - \text{ADF (partial seizures) at Analysis Visit 3 (Study Visit 6)}}{\text{ADF (partial seizures) at Baseline Period}} \times 100$$

where Baseline Period (representing the whole 48 hours video-EEG data collection period) is the visit just before start of administration of study medication (Baseline).

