3.2.5.2 Adjusted Age

Pre-Term birth will be accounted for by using the adjusted age which is defined as

- $[(\text{Date} - \text{Date of Birth}) - (36 - \text{number of weeks pre-term}) \times 7] / 30.4375$
for subjects of chronological age < 12 months and
- Chronological age, otherwise

If not specified otherwise, adjusted age at the date of the assessment is used for all analyses.

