4.8 Examination of Subgroups

In this study 4 age categories will be investigated: 1 month to <6 months, 6 months to <1 year, 1 year to <2 years, and 2 years to <4 years. For the primary efficacy variable the data of the two youngest age categories will be pooled and data of the primary efficacy variable will be summarized by the so-obtained 3 age-categories and overall.

Note: for the age classification, the age at entry into study is used (Section 3.2.5.3).

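### SAP 8.3.1 does not determine which video-EEG seizures are counted up to 6 months of age; on the reading that SAP 8.4 supports, it also leaves open a change of counting rule within a child

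*SAP*

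**What the plan says.** SAP 8.3.1 defines the numerator of the video-EEG ADF. The lead sentence announces an age rule: "Partial seizure count will be based on electrographic seizures with or without clinical correlate depending upon age as specified below". Two rules follow.

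- Younger band: "Aged ≥1 month to ≤6 months will be based on electrographic seizures with an accompanying clinical correlate". This rule then cites two CRF items, one labelled "Number of electrographic seizures (Partial Onset Seizure only" and the other its electro-clinical counterpart, joined by the word respectively.
- Older band: "Aged >6 months to <4 years will be based electro-clinical seizures", with the electro-clinical CRF item alone.

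The ADF is derived separately at each time point: "x = -1 (Baseline), 1, or 3; and". Section 8.3.1 does not say at what date age is taken. SAP 3.2.5.2 gives the general default: "If not specified otherwise, adjusted age at the date of the assessment is used for all analyses". SAP 4.8, on the four age subgroups, carries the note that "for the age classification, the age at entry into study is used".

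The current protocol does not settle the count. Its Section 9 covers only the diary, and Sections 4.1.1.3.1 and 4.1.2.3.1 list the ADF variables without a counting rule.

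**The concern.** A programmer cannot derive the ADF for an infant of 6 months or younger from this text. The lead sentence requires the two bands to differ, the younger rule makes them the same, and the two CRF items give one band two candidate numerators.

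If the younger band is counted on all electrographic seizures, a second question follows: does a child who passes 6 months during the Evaluation Period keep the baseline rule? If not, part of that child's percent reduction is a change of definition. It would always favour levetiracetam, because the later count is the narrower one. The tables in SAP 8.3.2 pool all ages, so it would not be visible there.

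**Working it through.** The plan states no figure on this point, so there is none to reproduce. The check compares the texts and then does simple arithmetic.

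**1. Is the count determined?** Taking the words in SAP 8.3.1 as they stand:

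| Text | Count it implies up to 6 months |
|---|---|
| Lead sentence | Differs from the older band |
| Younger rule, words | Electrographic with a correlate, the same as the older band |
| Younger rule, first CRF item | All electrographic |
| Younger rule, second CRF item | Electro-clinical |

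These cannot all hold, so the numerator is not determined.

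**2. Which reading fits the rest of the SAP?** Section 8.4 plans one ADF listing for partial seizures and another for electro-clinical partial seizures. If both bands used electro-clinical counts, the two would carry the same count for every child. They differ only if the younger band uses electrographic seizures with or without a correlate. The text that Protocol Amendment 3 removed from protocol Section 9 is consistent with this, but it is superseded and serves only as background.

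**3. Who could change band, on that reading?** Inputs: baseline EEG at Visit 2, taken as Day -2 or Day -1; Visit 6 at target Day 43, window Day 39 to 47, with no Day 0 (SAP Table 3-1); 30.4375 days per month (SAP 3.2.5.1).

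Interval = Visit 6 day - baseline day - 1.

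- Shortest: 39 - (-1) - 1 = 39 days; 39/30.4375 = 1.28 months.
- Longest: 47 - (-2) - 1 = 48 days; 48/30.4375 = 1.58 months.

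An infant crosses 6 months if aged 6.0 months or less at the baseline EEG and more than 6 minus the interval. At target Day 43 the lower limit is 6 - 44/30.4375 = 4.55 or 6 - 43/30.4375 = 4.59 months. Over the visit window it runs from 4.42 to 4.72 months. These ages take adjusted age as moving with the calendar around 6 months; step 5 shows what the printed formula does.

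**4. How large would the artefact be?** Let E be the electrographic rate at both EEGs and f the share with a clinical correlate. The baseline count is E and the Visit 6 count is fE.

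Apparent reduction = 100 x (E - fE)/E = 100 x (1 - f).

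With a true 40% reduction, the figure shown is 100 x (1 - 0.6f). The documents do not give f; the range below is assumed.

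| f | No true change shows as | True 40% shows as |
|---|---|---|
| 0.90 | 10% | 46% |
| 0.75 | 25% | 55% |
| 0.50 | 50% | 70% |
| 0.25 | 75% | 85% |

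With one rule kept for all of a child's EEGs, the artefact is 0 for every f. If both bands require a correlate, it is also 0.

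**5. What does the printed adjusted age do?** Below 12 months of chronological age, SAP 3.2.5.2 subtracts (36 - weeks pre-term) x 7 days. With 0 weeks pre-term this is 252/30.4375 = 8.28 months. Adjusted age is then 6 - 8.28 = -2.28 months at chronological 6 months, and 11.99 - 8.28 = 3.71 months just before 12 months, after which chronological age applies. Taken literally, a term infant would change band at about 12 months, not 6. Age at entry (SAP 3.2.5.3) uses the same formula.

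**The case against.** The strongest reply is that the rule change is not established. On the quoted words of the younger rule, both bands use electro-clinical seizures and nothing happens at 6 months. SAP 4.8 also mentions age at entry, which may be the exception that the default allows. Both arguments stand in part. The change of rule is conditional on the reading in step 2. The SAP 4.8 note is attached to the four age subgroups, which cut at under 6 months, whereas SAP 8.3.1 includes 6 months in the younger band and does not cite the note. It is arguable, but it does not clearly override the default.

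A second reply is that little depends on this. ADF is an other efficacy variable, summarised descriptively, and limited to EEGs recorded before Protocol Amendment 3. SAP 3.1 anticipates few subjects in the youngest categories. The number who cross 6 months with usable EEGs at both times is not given and could be zero. SAP 8.4 also lists both seizure counts by subject and visit, so a reader could recompute. All of this stands. It limits the consequence but does not supply a definition.

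A reader might infer two further faults. One is that electro-clinical seizures are counted twice, by adding the two CRF items. No text says that the items are summed. The other is that the restriction to ILAE codes IA, IB and IC leaves out seizures seen only on EEG. That depends on how codes are assigned, which the documents do not show, and both CRF items are already confined to partial-onset seizures. Neither is claimed here.

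**Conclusion.** The SAP 8.3.1 rule for infants of 1 to 6 months contradicts its own lead sentence and names two CRF items for one band. That follows from the current text without assumptions.

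The possible change of rule is a second and conditional problem. It needs the electrographic reading of the younger band and age taken at each EEG. Given both, an infant from about 4.4 to 4.7 months up to 6 months at the baseline EEG could show a spurious reduction of 10% to 75% at Visit 6 over the assumed range of f. It would be wrong to state as fact that infants are counted by different rules at baseline and Visit 6: the documents permit that outcome but do not prescribe it, and the adjusted-age formula as printed would place the change near 12 months.

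Nor does the point reach the efficacy conclusion. That the video-EEG measure was once the primary endpoint describes a superseded plan. The primary analysis now rests on the diary and is unaffected. The correction is worth making because it removes a possible bias at almost no cost, but its reach is small.

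**What to change.** In SAP 8.3.1, name one CRF item per band:

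- up to 6 months: the electrographic partial-onset count, with or without a clinical correlate, not added to the electro-clinical item;
- above 6 months: the electro-clinical partial-onset count.

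State that each child's band is set once, by age at entry (SAP 3.2.5.3), and applied to the EEGs at Visits 2, 4 and 6 alike. Correct the adjusted-age formula in SAP 3.2.5.2, because age at entry depends on it; otherwise fixing the band at entry would fix the wrong band.

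If the sponsor did intend a correlate at every age, the lead sentence and the electrographic item should be removed instead. Either way, the choice should be recorded without reference to the EEG results.

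The cost is a few sentences of SAP text and the matching programming specification. No new data are needed.

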8.3.2 Other Efficacy Variables for Adjunctive therapy/Monotherapy

First Period:

The other efficacy variables for the First Period for the number of seizures based on the 48h video-EEG recorded prior to Protocol Amendment 3 are:

- Percent reduction in ADF of partial seizure frequency monitored by the 48h video-EEG at Analysis Visit 1 (Study Visit 4) and at Analysis Visit 3 (Study Visit 6) compared to Baseline. Percent reduction in ADF of partial seizure frequency will be summarized at Study Visit 4 and Study Visit 6 for all subjects combined.

A table Percent Reduction in Average Daily Frequency (ADF) of Partial Seizure Frequency at Analysis Visit 1(Study Visit 4) and Analysis Visit 3 (Study Visit 6), Adjunctive Therapy Subjects, presents summary statistics of subjects on adjunctive therapy for Analysis Visit 1 and Analysis Visit 3 on the FAS_A.

Note: This is combined over the age categories.

A table Percent Reduction in Average Daily Frequency (ADF) of Partial Seizure Frequency at Analysis Visit 1 (Study Visit 4) and Analysis Visit 3 (Study Visit 6), Monotherapy Subjects, presents summary statistics of subjects on monotherapy for Analysis Visit 1 and Analysis Visit 3 on the FAS_M.

Note: This is combined over the age categories.

- Percent reduction in ADF of partial seizure frequency monitored by the 48h video-EEG grouped into 6 categories: <0%, 0% to <25%, 25% to <50%, ≥50%, ≥75%, and 100% based on the Evaluation Period 48h video-EEG at Analysis Visit 1 (Study Visit 4) and Analysis Visit 3 (Study Visit 6) compared to Baseline.

A table Percent Reduction in Average Daily Frequency (ADF) of Partial Seizure Frequency Grouped into 6 Categories, Adjunctive Therapy Subjects, presents the number and percentage of subjects, on adjunctive therapy, for Analysis Visit 1 and Analysis Visit 3 within each of the above defined six categories for all analysis visits on the FAS_A.

Note: This is combined over the age categories.

A table Percent Reduction in Average Daily Frequency (ADF) of Partial Seizure Frequency Grouped into 6 Categories, Monotherapy Subjects, presents the number and percentage of subjects on monotherapy, for Analysis Visit 1 (Study Visit 4) and Analysis Visit 3 (Study Visit 6), within each of the above defined six categories for all analysis visits on the FAS_M.

Note: This is combined over the age categories.

Combined First and Second Periods:

The other efficacy variables for the combined First and Second Periods are:

- For each analysis visit, percent reduction in all types of seizure frequency per week from Baseline.

A table Percent Reduction in All Types of Seizure Frequency per Week during Combined First and Second Periods, Adjunctive Therapy Subjects presents summary statistics of subjects on adjunctive therapy, for each analysis visit on the FAS_A.

Note: This is combined over the age categories.

A table Percent Reduction in All Types of Seizure Frequency per Week during Combined First and Second Periods, Monotherapy Subjects presents summary statistics of subjects, on monotherapy, for each analysis visit on the FAS_M.

Note: This is combined over the age categories.

- For each analysis visit, percent reduction in all type of seizure frequency per week from Baseline grouped into 6 categories: <0%, 0% to <25%, 25% to <50%, ≥50%, ≥75%, and 100%.

A table Percent Reduction in All Types of Seizure Frequency per Week Grouped into 6 Categories During Combined First and Second Periods, Adjunctive Therapy Subjects, presents the number and percentage of subjects on adjunctive therapy within each of the above defined six categories for all analysis visits on the FAS_A.

Note: This is combined over the age categories.

A table Percent Reduction in All Types of Seizure Frequency per Week Grouped into 6 Categories During Combined First and Second Periods, Monotherapy Subjects, presents the number and percentage of subjects on monotherapy within each of the above defined six categories for all analysis visits on the FAS_M.

Note: This is combined over the age categories.

The following other efficacy variable is only applicable to Monotherapy:

- Percent of subjects who are continuously 6-months seizure-free monitored by the patient diary.

A subject is considered 6-months seizure free if they are seizure free for at least $26 \times 7 = 182$ consecutive days during the combined period of Evaluation Period + Dose adjustment Period + Maintenance Period, otherwise they are not considered seizure free.

The seizure free time interval must not contain days for which seizure data are missing, ie, “Not done” was checked on the Seizure Count CRF or seizure information is missing otherwise, eg because the complete and required CRF module was not filled out for a certain visit.

Subjects who received less than 182 days study medication are counted as not having achieved 6-months seizure freedom.

Missing seizure dates and dates for “not done” rows (in the following both are called “row”) are handled as follows:

- If the row date is missing completely (no entry), two cases can occur

1. The missing row date is in the first row of the CRF.
In this case, the visit date of the visit before the documentation visit is imputed.
2. The missing row date is not the first row of the CRF.
In this case, the date of the day after the last entry in the rows before the row with the missing date is imputed.

- If the row date is missing completely (“UNK”, ie, unknown), then the date of the visit before the documentation visit is imputed, independent of the row being the first row or a later one.
- If the year and month of a row date is present but the day is missing, then the same imputation as for a completely missing row date is performed first. If the imputed date is before the first of the month that is documented, then the first day of the month is used.
- If the year of a row date is present but the month is missing, then the same imputation as for a completely missing date is performed first. If the imputed date is before the first of the year that is documented, then the first day of the year is used.

A table Percent and Number of Subjects Who are continuously 6-Months Seizure-Free Monitored by Patient Diary During the Evaluation, Dose-adjustment and Maintenance Period presents the number and percentage of subject on monotherapy who are continuously 6-months seizure-free on the FAS_M.

Note: This is combined over the age categories.

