6.3 Withdrawal criteria

Subjects are free to withdraw from the study at any time, without prejudice to their continued care.

Subjects should be withdrawn from the study if any of the following events occur:

1. Subject must be withdrawn if there is an occurrence of status epilepticus, seizure clustering, or generalized tonic-clonic seizure, if unknown for the subject. If seizure frequency is increased, subject can be withdrawn for safety reasons, at the discretion of the Investigator.
2. Subject develops an illness that would interfere with his/her continued participation.
3. Subject is noncompliant with the study procedures or medications in the opinion of the investigator.

4. Subject takes prohibited concomitant medications as defined in this protocol.
5. Parent or legal guardian withdraws his/her consent.
6. The sponsor or a regulatory agency requests withdrawal of the subject.
7. Subject ≥ 6 years of age has active suicidal ideation without specific plan as indicated by a positive response (“Yes”) to question 4 of the “Since Last Visit” version of the C-SSRS. The subject should be referred immediately to a Mental Healthcare Professional and may be withdrawn from the study based upon the investigator’s judgment of benefit/risk of continuing the subject in the study/on study medication.
8. Subject ≥ 6 years of age has active suicidal ideation with a specific plan as indicated by a positive response (“Yes”) to question 5 of the “Since Last Visit” version of the C-SSRS. The subject should be referred immediately to a Mental Healthcare Professional and must be withdrawn from the study.
9. Subject who has cluster seizures prior to Visit 1 intermittently takes benzodiazepines, phenobarbital, or phenytoins more than 1 single administration per week during the study period.
10. Subject on monotherapy needs to add another AED during the First Period.

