7.8.1 Permitted concomitant treatments (medications and therapies)

First Period

Subjects on adjunctive therapy must be on a stable regimen of 1 or a maximum of 2 other AEDs for the Selection and Evaluation Periods (Appendix 3 [Section 17.3]). No new AEDs may be added or current AEDs discontinued for at least 2 weeks prior to Visit 1. Minor adjustments to the dose of current AEDs are allowed prior to Visit 1 only.

Subjects on adjunctive therapy who have VNS that have been implanted for at least 6 months prior to Visit 1 are allowed as long as the settings have been stable for at least 2 months prior to Visit 1. Activated VNS must be counted as 1 of the 2 AEDs.

The use of intermittent benzodiazepines, phenobarbital, and phenytoins is allowed as long as the frequency is not greater than 1 single administration per week for at least 2 weeks prior to Visit 1 and during the First Period. If benzodiazepines are used more than once a week, they must be considered as 1 of the AEDs.

Second Period

The Investigator (or designee) will be allowed to change the type, dosage and administration, or discontinue/resume concomitant AEDs to optimize tolerability and seizure reduction for each subject after 3 months of the start of the Second Period. Changes in concomitant AED(s) will be allowed only if the dose of LEV has been stable for the previous 2 weeks; LEV dose must remain stable during changes to concomitant AED(s). Subjects may take no more than 3 concomitant AEDs except when temporary (≤ 12 weeks) use of an additional AED is required to switch to a new AED (ie, taper from old AED during titration of new AED). New AED(s) may be added only when the subject has not optimally or adequately responded to a maximum tolerated dose of LEV. The concomitant AED(s) can be carefully tapered or discontinued at the discretion of the investigator. Monotherapy with LEV is permitted. Increasing the dose of LEV and/or concomitant AED(s), as well as addition of a new AED should be done at a visit (scheduled or unscheduled). There are no restrictions for concomitant AED(s) during the Down-Titration Period, considering subject safety.

The use of intermittent benzodiazepines, phenobarbital, and phenytoins is allowed as long as the frequency is not greater than 1 single administration per week during the Second Period. If benzodiazepines are used more than once a week, they must be considered as 1 of the AEDs.

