2.3.2 Adjunctive Therapy and Monotherapy

Subject who took at least 1 AED at Visit 1 will be categorized as a subject on adjunctive therapy, otherwise the subject will be categorized as on monotherapy (See Section 6.8 for identification of AEDs).

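### The monotherapy six-month seizure-freedom count has no rule for AEDs added in the Second Period, so the table cannot separate success on LEV alone from success on combination treatment

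*SAP*

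**What the plan says.** SAP 8.3.2 gives the rule, for the monotherapy group only: "A subject is considered 6-months seizure free if they are seizure free for at least $26 \times 7 = 182$ consecutive days". The window in which such a run may fall is wide: "during the combined period of Evaluation Period + Dose adjustment Period + Maintenance Period". Two conditions limit it. On diary data: "The seizure free time interval must not contain days for which seizure data are missing". On exposure: "Subjects who received less than 182 days study medication are counted as not having achieved 6-months seizure freedom". Neither concerns other AEDs. The planned table "presents the number and percentage of subject on monotherapy who are continuously 6-months seizure-free on the FAS_M".

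Group membership is decided once, in SAP 2.3.2: "Subject who took at least 1 AED at Visit 1 will be categorized as a subject on adjunctive therapy"; everyone else is monotherapy. FAS_M (SAP 3.5.3) needs only membership of SS_M and one post-baseline efficacy assessment. No section reclassifies a subject later.

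Protocol 6.3, criterion 10, is a reason for withdrawal: "Subject on monotherapy needs to add another AED during the First Period". It stops at the end of the First Period. For the Second Period, protocol 7.8.1 permits changes to concomitant AEDs after 3 months, with the LEV dose stable for the previous 2 weeks, and says: "New AED(s) may be added only when the subject has not optimally or adequately responded to a maximum tolerated dose of LEV". Protocol 7.8.2 prohibits no concomitant treatment in that period.

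**The concern.** The protocol makes inadequate response to LEV the condition for adding an AED. A subject who meets that condition, starts a second drug and then has 182 clean days enters the table as a seizure-free monotherapy subject. A subject who was seizure-free on LEV alone enters in the same cell, and the table gives no means of telling them apart.

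This matters because other monotherapy evidence is thin. Protocol 4.1.2 defines no primary variable for this group and no secondary variable for the First Period, while the indication described in the protocol summary includes monotherapy. The long-term FAS_M results are likely to be quoted as evidence on LEV monotherapy, and this count does not isolate it.

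**Working it through.** **The plan's own figure.** 26 × 7 = 182 days, as stated in SAP 8.3.2.

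**Inputs**
- Visit 6: target Day 43, window Day 39 to 47 (SAP Table 3–1).
- The Maintenance Period starts the day after Visit 6 (SAP 3.2.1.2.1.2).
- For subjects enrolled before Amendment 3 as video-EEG failures, the Second Period starts on Day 1 (SAP 3.2.1.2.2.2 and Table 3–1).
- Data cut-offs: final subject at Visit 13 (target Day 183) and at Visit 16 (target Day 351) (SAP 4.3 and Table 3–1).
- Planned monotherapy subjects: 10 (protocol 5.1.5, SAP 2.3).
- Assumption: 3 months = 3 × 30.4375 = 91.3, taken as 91 days.
- Assumption: the 3-month limit applies to adding an AED as well as to changing one, and applies equally to the video-EEG failures. If addition could come sooner, the days below move earlier.

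**Earliest day an AED can be added** = first day of Second Period + 91
- First Period completers: 44 + 91 = Day 135 (40 + 91 = 131 to 48 + 91 = 139 over the Visit 6 window).
- Video-EEG failures: 1 + 91 = Day 92.

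**Earliest end of a run wholly on combination treatment** = day of addition + 181
- Completers: 135 + 181 = Day 316 (312 to 320). This is before the Visit 16 target of Day 351.
- Video-EEG failures: 92 + 181 = Day 273.

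**The same subject on a LEV-alone count.** A completer who adds an AED on Day 135 has at most 134 earlier days (130 to 138 over the window). That is below 182, so the subject would not qualify.

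**Dependence on follow-up.** The latest start of a qualifying run is the last day of follow-up − 181.
- Followed only to Visit 13: 183 − 181 = Day 2. No run can lie wholly after addition. At most 183 − 135 + 1 = 49 days of a completer's run could follow it.
- Followed to Visit 16: 351 − 181 = Day 170. An AED added between about Day 135 and Day 170 leaves room for a run wholly on combination treatment. Later additions need longer follow-up, which the open-ended Maintenance Period can supply.

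**Direction and size.** Every LEV-alone run of 182 days also satisfies the current rule, and the denominator is the same. The current count therefore cannot fall below the LEV-alone count. With 10 subjects, each subject who qualifies only through days after addition moves the result by 1/10 = 10 percentage points. To illustrate, going from 3/10 to 4/10 changes 30% (exact 95% CI 6.7 to 65.2) to 40% (12.2 to 73.8). The documents give no rate of AED addition, so the total effect cannot be computed.

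**The case against.** A reader might infer that the variable contradicts its objective and is simply biased upwards. The documents do not support that. The objective confined to monotherapy (second bullet of protocol 3.2 and SAP 2.1.2) covers the First Period only, where criterion 10 withdraws subjects who need another AED. This variable belongs to the combined First and Second Periods, whose efficacy objective covers both monotherapy and adjunctive use. Monotherapy is a group label defined at Visit 1, and Protocol Amendment 1 deliberately narrowed criterion 10 to the First Period. Seizure freedom whatever AEDs are added later, in subjects who entered without an AED, is a legitimate question. Upward bias arises only if the figure is read as the effect of LEV alone. This objection stands, and it is why the defined count should stay.

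Two further objections carry some weight. First, SAP 6.8 already tabulates concomitant AEDs and lists those started on or after the first dose, and SAP 8.4 lists dated seizure counts, so with about 10 subjects an affected responder could be traced by hand. That lessens the consequence, but none of these outputs feeds the percentage. Second, this is an untested variable in the lowest efficacy tier, and SAP 8 treats everything outside the testing hierarchy as exploratory. That is correct and limits the importance of the point.

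**Conclusion.** The gap is real and small. SAP 8.3.2 has no rule for added AEDs, and a 182-day run wholly on combination treatment can be counted as monotherapy seizure freedom. For First Period completers this needs follow-up to about Day 316; for earlier video-EEG failures, to about Day 273. It cannot happen for a subject followed only to Visit 13.

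As a count regardless of later AEDs, the figure is valid. As an estimate for LEV alone it can only be too high, by 10 percentage points per affected subject if 10 are enrolled. The number affected is not given and may be zero. The dates rest on 3 months being 91 days and on the 3-month limit covering additions. Nothing here bears on the primary analysis. The point is a cheap improvement in what the table tells its reader.

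**What to change.** In SAP 8.3.2, keep the defined count and label it as seizure freedom regardless of added AEDs. In the same table add a LEV-alone row, with the same FAS_M denominator, in which a subject's run ends at the start date of the first added AED. A subject who completed 182 clean days before that date still counts.

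Identify added AEDs through the review already set out in SAP 6.8.1, which looks at name, frequency and formulation. Exclude the intermittent use that protocol 7.8.1 permits. Base any statement about LEV monotherapy on the LEV-alone row.

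The start dates are already collected, so the cost is a little programming. The LEV-alone percentage may be lower than the other row. No new data are needed, and subject management does not change.
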